8. ANALYSIS METHODS

8.1. Study Subject Data

8.1.1. Subject Disposition

Summaries of analysis population membership and final subject status (completed or withdrawn), including reasons for withdrawal, will be produced based on the number of randomized subjects. The number of subjects screened will be provided. Data will be presented by treatment group as well as overall for the study, with exception of the number of screen failures (to be displayed without respect to treatment).

Screen failures, analysis populations, and final subject disposition status will be listed.

8.1.2. Protocol Deviations

Protocol deviations will be identified and classified as important or not important. Important protocol deviations may include but are not limited to:

- Violation of Inclusion/Exclusion Criteria
- Study drug compliance $\leq 80\%$ or $\geq 120\%$
- Use of prohibited therapies
- Incorrect treatment

Important protocol deviations deemed to possibly affect the efficacy measurements or integrity of any other key study data may be identified prior to database lock to support defining the PP population.

Sponsor: Sagimet Biosciences
Protocol Number: 3V2640-CLIN-005
Version and Date: Final Version 1, 02June2020

Protocol deviations including category will be summarized by treatment group and overall for the study. Protocol deviations due to COVID impact will be identified as such.

A listing of protocol deviations will be provided.

8.1.3. Demographic and Baseline Characteristics

Subject demographics will be summarized and listed. Age, sex (Male / Female), ethnicity (Hispanic or Latino / Not Hispanic or Latino), race (American Indian or Alaska Native / Asian / Black or African American / Native Hawaiian or Other Pacific Islander / White / Other), baseline height (cm), baseline weight (kg), body mass index (BMI) (kg/m²), Type 2 Diabetes Mellitus status (Yes / No), waist circumference (cm), hip circumference (cm), waste-hip ratio (cm) and country (US / China). Age will also be categorized as a categorical variable (< 65, 65 ≤ age < 75, 75 ≤ age < 85, ≥85) for reporting. Data will be presented by treatment group as well as overall for the study.

The following conversions and equations will be used as applicable:

$$\text{BMI (kg/m}^2\text{)} = \text{weight(kg)}/[\text{height(m)}^2]$$

Demographic and baseline characteristics summaries will be provided for the mITT, and safety populations. Subgroup analyses will be produced by region (US/China).

Baseline characteristics including social history (tobacco, alcohol, and caffeine use) will be listed. Pregnancy test, breath/blood alcohol test, and beta-human chorionic gonadotropin (β-HCG) data will be listed. NASH confirmation data collected at screening will be presented in a data listing.

8.1.4. Medical History

Medical history will be coded using the Medical Dictionary for Regulatory Activities (MedDRA) version 22.0 Mar 2019 for reporting by system organ class (SOC) and preferred term (PT). Medical history data will be presented in a listing.

8.1.5. Prior and Concomitant Medication

The incidence of medication use will be summarized by WHO Drug Dictionary anatomic therapeutic class (ATC) Level 2 classification (i.e. therapeutic main group) and preferred name. A subject will be counted only once at each level of reporting. Prior medications are medications that have been discontinued prior to the treatment start date (e.g. taken exclusively during the pre-therapy period). Concomitant medications are medications taken at any point during the on-therapy or post-therapy periods. Subjects could start a concomitant medication prior to study start which is ongoing at time of first treatment or subjects could start a new medication during the on-therapy or post-therapy periods.

Concomitant medication use will be summarized separately and presented by treatment group for the ITT population.

Sponsor: Sagimet Biosciences
Protocol Number: 3V2640-CLIN-005
Version and Date: Final Version 1, 02June2020

All prior and concomitant medication data will be listed including the verbatim and preferred drug name and ATC Level 2.

8.2. Study Drug Exposure and Compliance

Duration of drug exposure will be summarized both as a continuous and a categorical variable for the safety population. Exposure will be calculated as:

$$\text{study drug stop date} - \text{study drug start date} + 1 \text{ [converted to weeks (days divided by 7)]}$$

Categories for reporting exposure will include < 2 weeks; 2 weeks - <4 weeks; 4 weeks - <8 weeks; 8 weeks - <12 weeks; \geq 12 weeks.

Drug accountability is captured in the eCRF at each visit. The eCRF captures the number of pills dispensed, the number returned, and the number missed during the dosing period. Overall compliance will be determined based on pill counts over each visit period and taking into account the number missed. Compliance will be derived as:

$$\frac{[(\text{# of pills dispensed} - \text{# of pills returned}) - \text{# of missed pills}]}{\text{number of days within the visit period}} \times 100$$

Where number of days within the visit period is derived as:

$$\text{Date of Visit (X+1)} - \text{Date of Visit (X)} + 1$$

Compliance will also be summarized for the following categories < 80%, 80% - 120%, and > 120%.

Mean daily dose (mg) and total cumulative dose (mg) received will also be summarized. Total cumulative dose will be summarized overall and separately for those that had extended dosing.

Listings of planned and actual treatments, overall compliance, and drug exposure will be produced.

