Lymphocyte subsets in peripheral blood mononuclear cells (Cohorts 1 and 2 only) ^{22,26}		X						X		
Sample for storage ^{22,27}		X						X	X	
Spot urine sample collection for:										
Exploratory PD biomarkers ²²		X						X	X	
Study Drug Administration										
Randomization		X ²⁸								
Study drug dispensation		X			X	X				
Study drug administration		QD PO from Day 1 through Week 12								
Study drug accountability				X	X	X	X	X		

Table footnotes appear on the following page.

- 1 Baseline evaluations are to be performed pre-dose, unless otherwise specified.
- 2 At the time of this amendment, subject participation in the 25 mg cohort is complete, with participation in the 50 mg cohort fully enrolled but with subject participation ongoing. The Sponsor notes that the COVID-19 pandemic may impact the conduct of the 50 and 75 mg cohorts, with challenges potentially arising from quarantines and travel limitations affecting study subjects as well as clinic and imaging facility closures. Accordingly, safety assessments scheduled for the Week 12 and 16 visits, including sample collection for clinical laboratory tests, physical examinations, and documentation of AEs, may be performed at an alternate study center or by home health care visit. Furthermore, if the subject is unable to attend the Week 12 visit at the study center, one MRI-PDFP may be performed at any time between Week 11 and 16. If this scan is performed after Week 12, the subject must continue to receive study drug until the final scan is performed; however, study drug is not to be continued for >16 weeks. The safety of subjects who continue dosing beyond 12 weeks will be assessed during this continued dosing period by planning for blood sample collection at an alternate site or home visit at Week 12 and blood sample collection and physical examination on the last day of dosing. A 4-week off treatment safety assessment is to occur after the last dose, regardless of whether a subject receives treatment for 12 or 16 weeks.
For subjects in Cohort 3, Week 16 assessments may serve as screening assessments if within the window before the Day 1 visit.

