5. ANALYSIS POPULATIONS/SETS

The modified intent-to-treat population (mITT) is defined as all subjects who are randomized, receive study drug for at least 8 weeks, and have a baseline and at least 1 post-baseline MRI-PDFF assessment on or after Week 8. The mITT is the primary population for analysis of MRI-PDFF assessments and subjects will be analyzed according to the randomized treatment assignment.

The intent-to-treat population (ITT) is defined as all subjects who are randomized and received at least 1 dose of study drug. The ITT will be used for analysis of a subset of secondary efficacy endpoints and supportive and sensitivity analyses of MRI-PDFF assessments. Subjects will be analyzed according to the randomized treatment assignment.

The as-treated population (ATP) is defined as all subjects who are randomized and received at least 1 dose of study drug. The ATP will be used for analysis of secondary efficacy endpoints and supportive and sensitivity analyses of MRI-PDFF assessments. Subjects will be analyzed according to the treatment received.

The safety population is defined as all subjects who are randomized and received at least 1 dose of study drug and will be used for all analysis of safety. Subjects will be analyzed according to

the treatment received. If all subjects were dosed according to randomized treatment assignment, then the safety population and ITT are identical.

A per-protocol (PP) population may be defined for sensitivity analyses of the efficacy endpoints. The PP population will be based on subjects in the mITT population with data excluded from subjects who have important protocol violations deemed to possibly affect the efficacy measurements or integrity of any other key study data. Subjects will be analyzed according to the actual treatment received. If a PP population is implemented, details on subjects excluded will be provided in the CSR.

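### SAP 8.2 compliance formula counts shared visit days twice and divides by days instead of scheduled tablets: slightly low at one tablet daily, and about doubled at 75 mg if the two strengths are pooled

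*SAP*

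**What the plan says.** SAP 8.2 sets out the derivation. "Overall compliance will be determined based on pill counts over each visit period and taking into account the number missed". The numerator is tablets dispensed minus tablets returned, minus tablets missed. The denominator is a number of days: "Where number of days within the visit period is derived as" the next visit date minus the current visit date, plus 1. The section gives no rule for combining periods into one overall value and has no term for tablets per day.

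The result is used in two places:
- SAP 8.2: "Compliance will also be summarized for the following categories" below 80%, 80% to 120%, and above 120%.
- SAP 8.1.2: "Important protocol deviations may include but are not limited to" a list that contains compliance at or below 80%, or at or above 120%. Deviations of this kind may support the per-protocol set, which SAP 5 leaves optional: "A per-protocol (PP) population may be defined for sensitivity analyses of the efficacy endpoints".

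Protocol 9.5 gives one tablet daily for placebo, 25 mg and 50 mg, and two tablets of different strength for 75 mg. Protocol 9.6 allows a 75 mg subject to be reduced to one tablet. SAP Addendum 1 is to be read with the main SAP, summarizes the thirteen Cohort 3 subjects in a similar way using the earlier output design, and plans Table 14.1.7 on exposure and compliance. It gives no replacement formula.

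**The concern.** Adding 1 is right for a single closed interval, as in the exposure formula of the same section. It is not right for adjoining intervals. The visit that ends one period starts the next, so its date enters both denominators although only one dose is due that day. After Day 8 dosing is in the evening (Protocol 9.5), so a clinic-day dose normally belongs to the later period only.

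Separately, days equal scheduled tablets only when one tablet is due per day. That held for every regimen in SAP version 1. It does not hold at 75 mg.

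At stake are the values in the compliance table, the assignment to compliance categories, and the flagging of subjects close to 80%.

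**Working it through.** The plan states no compliance figure to reproduce, so the formula is applied to a subject with known adherence.

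**Inputs**
- 12 weeks once daily = 84 doses due (Protocol 9.5).
- Four periods if they follow the "Study drug accountability" row of Protocol Table 2, read as Weeks 2, 4, 8 and 12. Three if they follow dispensing at baseline, Week 4 and Week 8. One if Day 1 to Week 12 is treated as a single span.
- Assumption: tablets and days are summed over periods. Interior visit dates then cancel, so it does not matter that SAP 8.4 equates Week 2 with Day 8.
- Assumption, taken both ways: the last dose falls on the day before the final visit (visit on Day 85) or on the visit day itself (Day 84). Table 2 has dosing run through Week 12, which does not settle it.

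**One tablet daily**

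Denominator = (final visit day − 1) + number of periods.

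| Periods | Last dose day before final visit | Last dose on final visit day |
|---|---|---|
| Four | 84/(84+4) = 84/88 = 95.5% | 84/(83+4) = 84/87 = 96.6% |
| Three | 84/(84+3) = 84/87 = 96.6% | 84/(83+3) = 84/86 = 97.7% |
| Single span | 84/(84+1) = 84/85 = 98.8% | 84/(83+1) = 84/84 = 100% |

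The excess is therefore one day per period in the first column and one day fewer in the second.

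**Missed doses at which the 80%-or-less criterion is met**

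Correct value: 17 missed (67/84 = 79.8%; 68/84 = 81.0% is above it). As written:
- denominator 88: 14 missed, 70/88 = 79.5% (true 70/84 = 83.3%)
- denominator 87: 15 missed, 69/87 = 79.3% (true 69/84 = 82.1%)
- denominator 86: 16 missed, 68/86 = 79.1% (true 81.0%)
- denominator 85: 16 missed, 68/85 = 80.0% (true 81.0%)
- denominator 84: 17 missed, as it should be.

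**Other ways of combining periods** (last dose the day before the final visit). The unweighted mean of the four period values, with Week 2 on Day 15, is 94.9%. Treating Day 2 as a fifth period gives 84/89 = 94.4% pooled, or 85.9% as an unweighted mean.

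**75 mg, strengths pooled** (2 × 84 = 168 tablets due)
- Full adherence: 168/88 = 190.9% or 168/87 = 193.1%. With the last dose on the final visit day: 168/87 = 193.1% or 168/86 = 195.3%.
- Half adherence, 84 of 168 tablets: 84/88 = 95.5% or 84/87 = 96.6%, reported within 80%-120%.
- Dosing on 66 of 84 days (true 78.6%): 132/88 = 150.0% or 132/87 = 151.7%, reported above 120%. The mean daily dose, 66 × 75/84 = 58.9 mg, would still show the shortfall.
- With denominator 88, the 80%-120% category holds subjects who took 71 to 105 of 168 tablets (true 42.3% to 62.5%).
- Reduced to one tablet from Day 43, all taken: 42 × 2 + 42 = 126 tablets; 126/88 = 143.2% or 126/87 = 144.8%.

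If each strength is scored separately there is no doubling: 84/88 = 95.5% or 84/87 = 96.6% for each.

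**Both corrections are needed.** Removing only the plus 1 leaves 75 mg at 168/84 = 200%. Correcting only for tablets per day leaves 168/176 = 95.5% or 168/174 = 96.6%. Doing both gives 84/84 and 168/168 = 100%.

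**The case against.** The strongest case against has three parts.

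**The one-tablet figures depend on conventions the SAP does not state.** This stands. A reader might infer that every period is one day too long whatever the schedule, or that 98.8% is the smallest possible error. Neither is supported: if the last dose is taken on the final visit day, the plus 1 is correct for the last period, and a single span reads exactly 100%. But a single span does not fit a formula defined over each visit period, and with three or four periods the value is low under either assumption.

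**The 75 mg doubling is conditional.** This also stands. A reader might infer that Cohort 3 compliance will certainly be reported near 190%. The documents do not show how tablet counts of the two strengths were captured, and the addendum promises similar summaries, with changes to be described in the study report. Later disclosure is not a prespecified formula, however, and the only formula given fails for two tablets if counts are pooled.

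**Little follows from it.** Largely true. Fully adherent 25/50 mg subjects stay within 80%-120%, the deviation list is permissive, and the per-protocol set is optional and for sensitivity only. Cohort 3 is descriptive with no per-protocol output planned, and values near 190% would be noticed. In addition, "Mean daily dose (mg) and total cumulative dose (mg) received will also be summarized", and the accountability, administration and dosing-adjustment listings would show under-dosing. What remains is that half adherence at 75 mg would look unremarkable in the category table.

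**Conclusion.** Minor; wrong as written. The derivation, followed literally, does not return 100% for a fully adherent subject seen over several visit periods.

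- One tablet daily: 95.5% or 96.6% (four or three periods, last dose the day before the final visit), or 96.6% or 97.7% (last dose on that day). The lower deviation cut-off moves from 17 missed doses to 14-15, or 15-16. These figures rest on 84 doses and pooling over periods.
- 75 mg: about 191-193% for full adherence and about 95-97% for half adherence, only if the two strengths are pooled. The three categories then misclassify the cohort.

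The effect stops at compliance and deviation summaries and, for 25/50 mg, the optional per-protocol set. A reader might infer bias in the efficacy result or between arms. The primary mITT analysis does not use this compliance derivation, and no difference by arm can be quantified from the documents. Nor do they show that missed tablets are subtracted twice: that happens only if a missed tablet is also counted as returned, and no figure here assumes it.

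**What to change.** In SAP 8.2, define compliance as tablets taken divided by tablets scheduled at the recorded dose in force, times 100. Use non-overlapping periods: next visit date minus this visit date, with the final period ending on the last scheduled dosing day, inclusive. That inclusive end keeps a dose taken on the final visit day in the denominator. Sum numerator and denominator over periods for the overall value.

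In the addendum, state that the two 75 mg strengths are both included in tablets scheduled, or are scored separately. Take tablets scheduled from the dosing record, so that a subject reduced to one tablet is scored against one.

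Two clarifications can be made at the same time: say what counts as a missed tablet so that a returned one is not subtracted again, and align the boundaries in SAP 8.1.2 and 8.2, which differ only at exactly 80% and 120%.

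Cost: one formula, a few lines of text, and reprogramming of one derivation. No new data are needed.

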8.6. Subject Withdrawal Criteria

Subjects will be informed that they have the right to withdraw from the study at any time for any reason, without prejudice to their medical care. Study drug must be permanently discontinued

and the subject withdrawn from the study for any of the following TEAEs, with the subject managed as indicated:

- **Palmar-plantar Erythrodysesthesia (PPE):** For mild to moderate symptoms of PPE (e.g., redness, pain, or scaling of hands or feet), study drug should be interrupted and symptomatic measures, including hand cream such as “Udder Cream”, instituted immediately. Study drug may be resumed after resolution of symptoms. Study drug should be permanently discontinued at the first sign of significant/severe, redness, pain, or scaling of hands or feet, and symptomatic measures instituted immediately.
- **Dyspnea or suspected pneumonitis:** Study drug should be permanently discontinued for subjects with shortness of breath or other respiratory symptoms that are otherwise unexplained. The subject is to be carefully monitored for improvement. In the event that symptoms worsen or present as more than mild intensity, immediate referral to a qualified pulmonologist for definitive diagnosis and treatment should be undertaken.
- **Visual symptoms (including keratitis):** Study drug should be permanently discontinued at the first sign of significant, redness, pain, or dryness of the eyes. Symptomatic measures, including moisturizing eye drops should be instituted. In the event that symptoms worsen or present as more than mild, immediate referral to a qualified ophthalmologist should be undertaken.
- **Evidence of drug-induced liver injury (DILI);** Study drug should be permanently discontinued for subjects with evidence of DILI; see [Appendix A](#) for details.

Refer to the Study Manual for additional details regarding the assessment and management of these events.

Furthermore, the Investigator also has the right to withdraw subjects from the study for any of the following reasons:

- Progression of underlying disease that, in the opinion of the Investigator, precludes further study treatment.
- Occurrence of any other unacceptable AE.
- Study drug interruption for any reason for >7 days.
- Subject requires use of a prohibited concomitant medication or therapy.
- General or specific changes in the subject’s condition unacceptable for further treatment within the study parameters, in the judgment of the Investigator.
- Non-compliance.

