9.4. Study Drug Accountability

The US FDA, Chinese Food and Drug Administration (CFDA) and other applicable regulatory authorities require accounting of all investigational drug received by each study center. Records of drug disposition required include the date received by the center, date administered, quantity administered, and the subject to whom study drug was administered. The Investigator is responsible for the accountability of all used and unused study drug containers and unused study drug.

Each study center is to use a study drug accountability log to document study drug disposition. All items on this form are to be completed in full. The Sponsor's clinical research associate (CRA) is to approve the area where study drug is to be stored and accountability records are to be maintained.

The investigator identification number and subject initials (as allowed by local regulations) and identification number are to be recorded on each study drug accountability log. Each time study personnel dispense study drug for a subject, he or she is to record the date dispensed, amount of study drug dispensed, and his or her initials. Study personnel are to monitor the inventory of clinical supplies and maintain a count of all used and unused study drug. The CRA is to review study drug accountability records and remaining drug supplies during routine monitoring visits.

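### The SAP compliance formula subtracts a missed tablet twice if that tablet is also returned, so the 80% deviation limit acts at a true adherence between 80% and 90%, depending on the share returned

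*SAP*

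**What the plan says.** SAP section 8.2 describes the source data: "The eCRF captures the number of pills dispensed, the number returned, and the number missed during the dosing period". From these three counts, "Overall compliance will be determined based on pill counts over each visit period and taking into account the number missed". The formula takes dispensed minus returned, subtracts missed, divides by the number of days in the visit period and multiplies by 100. Days in the period are the difference between the two visit dates plus one. The section does not define a missed pill and does not say whether a missed tablet that is handed back is entered under both counts.

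The result is used in three places:

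- **Summary.** "Compliance will also be summarized for the following categories < 80%, 80% - 120%, and > 120" percent (SAP 8.2).
- **Deviations.** SAP 8.1.2 lists compliance of 80% or below, or 120% or above, among the possible important protocol deviations.
- **Per-protocol population.** Under SAP 8.1.2, important deviations judged to affect efficacy measurements or key data may be identified to support defining this population. SAP section 5 says the population may be defined, and SAP 8.3.1.2 repeats the primary analysis in it.

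On drug accountability, Protocol 9.4 states: "The Investigator is responsible for the accountability of all used and unused study drug containers and unused study drug". Site staff are also to keep a count of used and unused drug.

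**The concern.** A missed pill, in the ordinary sense, is a dose that was not taken. If its tablet comes back to the site it is part of the returned count, and dispensed minus returned has already removed it. Taking off the missed count as well removes it again. The second deduction is right only for a missed tablet that did not come back, and the formula does not separate the two cases.

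The 80% limit would then label some subjects as important deviators although they took clearly more than 80% of their doses. Reported compliance would be too low, and a per-protocol analysis using the limit could lose subjects it was meant to keep.

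**Working it through.** The 80% limit is a set rule, so the plan has no derived figure to reproduce. The check is algebra on the formula.

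**Inputs**

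- One tablet a day in Cohorts 1 and 2 (Protocol 9.5), so expected doses e equal dosing days; 84 for 12 weeks.
- m = missed doses.
- f = share of missed tablets returned. The documents do not give it, so the range 0 to 1 is shown.
- s = surplus tablets dispensed and returned unused.

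**Numerator**

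Dispensed = e + s. Returned = s + f·m. So dispensed − returned − missed = (e + s) − (s + f·m) − m = e − (1+f)·m. The surplus cancels. The number of doses taken is e − m, so the formula is exact at f = 0 and deducts 2m at f = 1. As an extreme check, a subject who takes 42 of 84 tablets and returns the other 42 scores (84 − 42 − 42)/84 = 0%, against a true 50%.

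**Where the 80% limit acts**

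Setting [e − (1+f)·m]/D = 0.80 gives m = (e − 0.80·D)/(1+f), and true adherence is 1 − m/e. D = e isolates the numerator. D = e + 1 is the SAP's denominator for one visit period, assuming the visit-day tablet is due in only one of two adjoining periods. Period lengths of 14 and 28 days are taken from visits at Weeks 2, 4, 8 and 12.

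| Share returned f | D = e | 14 days, D = 15 | 28 days, D = 29 |
|---|---|---|---|
| 0 | 80.0% | 85.7% | 82.9% |
| 0.5 | 86.7% | 90.5% | 88.6% |
| 1 | 90.0% | 92.9% | 91.4% |

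The rise down each column is the numerator effect. The rise from the D = e column to the other two comes from the added day, a separate bias in the same direction.

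**Whole treatment period, f = 1, D = 84**

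- SAP formula: (84 − 2m)/84 ≤ 0.80 when m ≥ 8.4, so from 9 missed doses. At m = 9 it gives 66/84 = 78.6%; true adherence is 75/84 = 89.3%.
- True adherence: (84 − m)/84 ≤ 0.80 when m ≥ 16.8, so from 17 missed doses (67/84 = 79.8%).

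**One 28-day period**

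30 tablets dispensed, 3 doses missed, 5 tablets returned (2 surplus and the 3 missed). SAP numerator: 30 − 5 − 3 = 22, and 22/28 = 78.6%. Tablets taken: 30 − 5 = 25, and 25/28 = 89.3%. With the SAP's 29 days these become 75.9% and 86.2%.

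**With the written denominator summed over four periods**

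Periods of 14, 14, 28 and 28 days give D = 84 + 4 = 88. At f = 1 the limit acts at 91.9% true adherence: m = (84 − 70.4)/2 = 6.8. Seven missed and returned tablets give (84 − 14)/88 = 79.5%, against a true 77/84 = 91.7%.

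**The case against.** The strongest reply is that the eCRF and its completion guidance are not among the documents. If they define a missed pill as a tablet neither taken nor returned, the formula is correct, and the SAP's phrase about taking the missed number into account can be read that way. Protocol 9.4 makes sites account for unused drug, but it does not say that every missed tablet comes back or that it is entered under both counts. This stands as a limit on size: f is unknown and may lie well below 1. It does not clear the text. Nothing in either document restricts missed pills to unreturned tablets, and a programmer following SAP 8.2 would deduct every missed dose.

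Three stronger readings are tempting, and the documents do not support them.

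- **That the limit simply acts at 90%.** That is the full-return case with expected doses as denominator. At half return it is 86.7%, and at none 80%.
- **That active-arm subjects are flagged more often.** Protocol 8.6 allows interruption for mild to moderate palmar-plantar erythrodysesthesia, after which "Study drug may be resumed after resolution of symptoms", and the protocol reports this event with TVB-2640 in earlier studies. But neither document says that interrupted doses are entered as missed pills, and the Cohort 3 addendum plans a separate listing of dosing adjustments. Neither gives interruption rates by arm. A 7-day interruption with full return scores (84 − 14)/84 = 83.3% on 84 days, which is not flagged, and 79.5% on 88 days, which is. A difference between arms is possible but not shown.
- **That the efficacy conclusion is at risk.** The primary and key secondary analyses use the mITT population, which depends on 8 weeks of drug and on scans, not on pill counts. The 80% rule excludes nobody automatically: the SAP says such deviations may count as important, may be identified for the per-protocol population, and that the population itself may be defined.

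**Conclusion.** The concern holds for the formula as written, on the ordinary meaning of a missed pill. The numerator falls short of tablets taken by f·m. With expected doses as denominator, the 80% limit acts at true adherence of 80%, 86.7% or 90% for f of 0, 0.5 or 1, and in the full-return case over 84 days from 9 missed doses instead of 17. These figures assume one tablet a day and that a returned missed tablet is entered under both counts.

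The consequence is confined to the compliance summary, the deviation flag and any per-protocol sensitivity analysis. It is worth correcting because it can mislabel subjects with close to 90% adherence, but it gives no reason to doubt the primary analysis.

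**What to change.** In SAP 8.2, define compliance as (tablets dispensed − tablets returned) / tablets planned in the period. Subtract missed tablets only where they were not returned, and define that term in the text. Apply the 80% deviation rule, and any per-protocol exclusion based on it, to the corrected value.

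SAP 8.2 names only dispensed, returned and missed counts, so it should not be assumed that the eCRF can identify missed tablets that never came back. If it cannot, drop the missed term and report missed doses separately. If the completion guidance already limits missed pills to unreturned tablets, keep the term and state that definition in the SAP.

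Planned tablets as the denominator also removes the extra day per period and suits the two-tablet 75 mg regimen in Protocol 9.5.

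The cost is a short change to SAP wording and programming. The downside is that, where unreturned missed tablets cannot be identified, they count as taken, and compliance is somewhat overstated for those subjects.
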